#### **4.4. Safety outcomes**

##### **Adverse events**

Adverse events are reported at each clinic visit (after 6 and 12 months follow-up) using administered questionnaires with open-ended questions. Adverse events are categorized into 10 subcategories (ranging from gastrointestinal issues to serious adverse events) and will be presented as both the total number of events in each diet group (n/%) and separately for each of the 10 events (n/%) at both 6 months- and 12 months follow up.

##### **Interim analysis**

No interim analysis will be performed.

#### **4.5. Co-interventions**

Information on co-interventions such as medication use and dietary supplements (among others) are reported at each clinic visit (after 6 and 12 months follow-up) using administered questionnaires with open-ended questions. Alcohol intake will be assessed using the concentration of the phosphatidylethanol biomarker in fasting blood samples and physical activity (step count) will be assessed using pedometers.

### **5. Populations and subgroups to be analyzed**

#### **5.1 Populations**

**Intention to treat (ITT):** All subjects randomized at baseline will constitute the ITT-population and will be the primary study population for the analyses. Missing data will be imputed as described in section 7 in this document.

**Per-protocol (PP):** All subjects completing the study period with complete data on the outcome of interest will constitute the PP-population. The PP-population will be the secondary study population for the analyses.

#### **5.2 Subgroups**

Further statistical analyses of the primary and secondary outcomes (liver fat, HbA1c and blood lipids) will be performed in the following prespecified subgroups:

**Type-2 diabetes status:** Subjects will be divided into two subgroups based on type-2 diabetes status (yes/no) of which the other subgroup (“no”) will constitute of subjects without type-2-diabetes but with prediabetes as defined by a fasting plasma glucose between 5.6-6.9 mmol/L and/or an HbA1c value between 39-47 mmol/mol. Type-2 diabetes diagnosis is verified by a clinician using medical records.

**Gender:** Subjects will be divided into two subgroups based on gender (male/female).

**NAFLD status:** Subjects will be divided into two subgroups based on NAFLD status (yes/no) in which NAFLD is defined as a liver fat content exceeding 5.56 % of liver tissue.

**PNPLA3 genotype:** Subjects will be divided into two subgroups based on the I148M variant of the PNPLA3 gene (CC vs CG/GG genotype).

**Compliers:** Subjects will be divided into two subgroups based on dietary adherence (high vs low compliers), assessed using both dietary and lipogenic biomarker changes (e.g. linoleic acid, DHA and palmitoleic acid) between month 0 and month 12.

All subgroup analyses will be conducted as described for the analyses of the full study population.

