## 1. Introduction

Randomized controlled studies investigating the impact of replacing dietary carbohydrates with polyunsaturated fat (PUFA) on liver fat content and cardiometabolic risk in individuals with prediabetes and T2D are lacking. Also, the effects of a Healthy Nordic Diet on liver fat content and glycemic control have not been investigated. This study therefore aims to:

- Investigate the effects of the diets on liver fat content (primary aim)
- Investigate the effects of the diets on pancreatic fat, visceral fat, lean tissue, glycemic and lipid control
- Investigate the effects of the diets on plasma markers of de novo lipogenesis (DNL) and desaturation (i.e. stearoyl-Coenzyme desaturase 1, SCD-1) as well as on hepatic DNL using MRI spectroscopy
- Investigate gene-diet interactions, especially if common gene variants (e.g. in PNPLA3) known to increase liver fat and dyslipidemia, may modify the dietary effects.
- Perform lipidomic analyses to identify potential mechanistic pathways that may associate with diet-induced changes in liver fat, pancreatic fat, visceral fat, insulin sensitivity, dyslipidemia or DNL

Our hypothesis is that a customized diet will effectively reduce liver fat through suppression of hepatic DNL and SCD-1 activity, and thereby improve atherogenic dyslipidemia, insulin resistance and hyperglycemia in individuals with prediabetes and T2D.

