### **Exclusion criteria**

- BMI  $>$ 40
- Alcohol intake  $>$ 20 g/day
- Unwillingness to follow a new prescribed diet for 1 year
- Diet-induced weight loss ( $\geq$ 10%) the preceding 3 months of screening
- Malignant disease
- Severe kidney and liver disease
- Heart failure or other severe CVD
- Claustrophobia or metal parts in the body (MRI)

Subjects enrolled in this study will be allocated to three different diet groups in a 1:1:1 allocation ratio using stratified randomization with type-2 diabetes status (yes/no) and gender (male/female) as stratifying factors. Subjects will be followed prospectively for 12 months.

The three diet-groups are:

**Experimental:** Customized diet to reduce liver fat

Ad libitum diet high in plant-derived PUFA and lower in carbohydrates

**Experimental:** Healthy Nordic diet

Ad libitum diet, based on Nordic foods, higher in carbohydrates (high fiber/low GI) and lower in fat but rich in monounsaturated fatty acids (MUFA) and PUFA

**Active Comparator:** Control

Ad libitum diet in accordance with the Nordic Nutrition Recommendations

Further details of each diet can be found in the study protocol registered at ClinicalTrials.gov (NCT04527965).

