- Between-group changes in circulating inflammatory markers (CRP, Tumor Necrosis Factor Alpha-receptor 1 and 2, Interleukin-1 receptor antagonist, Fibroblast growth factor 21) between baseline and month 12

[Time Frame: 12 months] [Unit: ng/l or mg/l (CRP)] [Variable: Continuous]

Assessed by routine clinical chemistry and ELISA

- Between-group changes in pancreatic fat between baseline and month 12

[Time Frame: 12 months] [Unit: %] [Variable: Continuous]

Assessed by magnetic resonance imaging (MRI)

- Between-group changes in flow-mediated dilation (FMD) between baseline and month 12

[Time Frame: 12 months] [Unit: %] [Variable: Continuous]

Assessed by ultrasound in approximately half of the study population (n=75)

- Between-group changes in pulse-wave velocity (PWV) between baseline and month 12  
[Time Frame: 12 months] [Unit: m/s] [Variable: Continuous]

Assessed by ultrasound in approximately half of the study population (n=75)

- Between-group values in FMD and PWV at month 12  
[Unit: % and m/s] [Variable: Continuous]

Assessed by ultrasound in the whole population (n=150)

- Between-group changes in liver fat, HbA1c, and blood lipids in prespecified subgroups of type-2 diabetes status (yes/no), gender (male/female), individuals with NAFLD/without NAFLD at baseline, individuals with the CC vs CG/GG I148M genotype in PNPLA3, and in individuals with low respectively high dietary compliance based on dietary and lipogenic biomarkers changes (e.g. linoleic acid, DHA and palmitoleic acid changes from baseline to 12 months) between baseline and month 12

[Time Frame: 12 months]

We will assess whether response to diets in liver fat, HbA1c and blood lipids differ between gender, high vs low compliers, genotype, individuals with prediabetes or diabetes or those who have NAFLD/do not have NAFLD at baseline

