#### 4.3. Exploratory outcomes

- Between-group changes in plasma and imaging-derived fatty acids and fatty acid ratios in the lipogenic pathway (i.e.16:1n-7, 18:1n-9, 16:0, 14:0, 18:0 and 16:1n-7/16:0, 16:0/18:2n-6, 16:1n-7/18:2n-6) between baseline and month 12

[Time Frame: 12 months] [Unit: %] [Variable: Continuous]

Fatty acids are measured as percentage change of all fatty acids, thus using one unit for the above five fatty acids. Assessed by gas chromatography (GC) and proton spectroscopy, and use of bioinformatic modelling (untargeted) to identify responders and non-responders in liver fat reduction and improvement in glycemic control and blood lipids (i.e. personalized medicine approach)

- Between-group changes in plasma lipids (ceramides) using a targeted lipidomic approach between baseline and month 12

[Time Frame: 12 months] [Unit: absolute and relative amounts] [Variable: Continuous]

Lipids are measured using ultra-high performance liquid chromatography coupled to tandem mass spectrometry (UPLC-MS/MS)

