### 6.1. Primary outcome

For the primary outcome a General Linear Model (GLM) will be applied using  $\Delta$ liver fat (%) between month 12 and baseline as the dependent variable, treatment group as factor and type-2 diabetes status (yes/no), gender (male/female) and baseline liver fat content (%) as included covariates. The GLM will be applied for the ITT-population (defined above) as well as for the PP-population (defined above). Independent samples post-hoc t-tests will follow if between-group statistical significance is observed.

A sensitivity analysis will be conducted for the primary outcome in both the ITT- and PP-population, with weight change included as an additional covariate in the GLM.

Treatment effects will be presented as mean or median differences (%) with 95% confidence intervals and with corresponding p-values.

When assumptions of the GLM are not satisfied, the Willett's residual method will be applied, followed by Mann-Whitney U post-hoc tests.

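### The high/low complier subgroup is defined by biomarker changes after randomisation that the diets are expected to cause, yet it is analysed between diets like the baseline subgroups, so its diet contrasts are not randomised comparisons.

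*SAP*

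**What the plan says.** Section 5.2 of the SAP names five prespecified subgroups for liver fat, HbA1c and blood lipids. Four are fixed before randomisation: diabetes status, gender, PNPLA3 genotype and NAFLD status (section 4.2 dates the last to baseline). The fifth is different: "Subjects will be divided into two subgroups based on dietary adherence (high vs low compliers), assessed using both dietary and lipogenic biomarker changes". The changes run from month 0 to month 12, and linoleic acid, DHA and palmitoleic acid are given only as examples.

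One sentence then covers all five: "All subgroup analyses will be conducted as described for the analyses of the full study population". For liver fat, section 6.1 specifies a general linear model with "treatment group as factor and type-2 diabetes status (yes/no), gender (male/female) and baseline liver fat content (%) as included covariates".

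Section 4.2 includes this in the secondary outcomes. It lists "individuals with low respectively high dietary compliance based on dietary and lipogenic biomarkers changes" among the subgroups and states the aim: "We will assess whether response to diets in liver fat, HbA1c and blood lipids differ between gender, high vs low compliers, genotype".

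Neither section gives a closed marker list, an expected direction for each diet, a threshold, a way to combine markers, or a choice between one common cut and arm-specific cuts. Neither says that the complier comparison is non-randomised.

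**The concern.** A subgroup comparison keeps the protection of randomisation only if allocation cannot affect who belongs to the subgroup. Here it can, and the SAP gives the reasons. One experimental arm is an "Ad libitum diet high in plant-derived PUFA and lower in carbohydrates". The introduction hypothesises that this customized diet will "effectively reduce liver fat through suppression of hepatic DNL and SCD-1 activity". Section 4.3 takes "fatty acids and fatty acid ratios in the lipogenic pathway" as exploratory outcomes, including 16:1n-7 (palmitoleic acid). Markers of the same kind thus serve both as effects of diet and as the basis of a subgroup.

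A control participant and a customized-diet participant who both rank as high compliers may have reached that rank for different reasons, so they need not be comparable in other respects. Adjusting for diabetes status, gender and baseline liver fat does not restore comparability on whatever else drives the marker. At stake is a secondary result that would appear beside the gender and genotype subgroups as if it had the same standing.

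**Working it through.** **Inputs from the SAP.** SD of liver-fat change 3, target difference 2 percentage points, 36 per group before drop-out (section 2.1); three arms allocated 1:1:1 (section 2). The section 2.1 figure reproduces: Lehr's formula gives 16 × (3/2)² = 36. The complier subgroup has no stated figure of its own.

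**Assumed, not in the SAP.** A single marker; a shift between an experimental arm and control of 0.5 to 1.5 SD; a within-arm correlation ρ of 0.3 to 0.5 between favourable marker change and fall in liver fat; no covariate adjustment.

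**Model.** Marker M = shift + Z. Liver-fat change Y = −3 × (ρZ + √(1−ρ²) e), with Z and e independent standard normal. As written, the diet has no effect on Y. A participant is a high complier if M exceeds a cut c. Among high compliers in an arm with shift s, the mean of Z is m(c − s), where m(x) = φ(x)/(1 − Φ(x)). Among low compliers it is −m(s − c).

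**Arm-specific median cuts, equal correlations.** The mean of Z is the same in every arm, so the bias is about 0. With unequal correlations the bias is 3 × (difference in ρ) × φ(0)/0.5. That is 3 × 0.2 × 0.798 = 0.48 for 0.5 against 0.3, and 3 × 0.5 × 0.798 = 1.20 for 0.5 against 0, with opposite signs in the two strata.

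**Common median cut, two arms only.** Here c is half the shift. For shift 1.0 and ρ = 0.5: m(0.5) − m(−0.5) = 1.141 − 0.509 = 0.632, and 3 × 0.5 × 0.632 = 0.95. Over the assumed ranges the false difference is 0.29, 0.57 and 0.85 (ρ = 0.3) or 0.48, 0.95 and 1.41 (ρ = 0.5) for shifts 0.5, 1.0 and 1.5, equal in both strata. Simulation with two arms of 50 gave matching values, and no bias when the shift was 0 or when all participants were analysed.

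**Common median cut, three arms, as in this trial.** The third arm moves the cut, so the two strata can differ. For shifts 0, 1.5 and 1.5 the cut is 1.044. Among high compliers, m(1.044) − m(−0.456) = 1.560 − 0.532 = 1.028, and 1.5 × 1.028 = 1.54.

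| Shifts (control, diet, third arm) | ρ | False difference, high | False difference, low |
|---|---|---|---|
| 0, 0.5, 0.5 | 0.3 | 0.29 | 0.28 |
| 0, 1.5, 0.5 | 0.5 | 1.36 | 1.46 |
| 0, 1.5, 1.5 | 0.5 | 1.54 | 1.26 |

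The differences are positive: the diet looks worse than control in both strata although it has no effect.

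**Same cut, marker on the causal path.** The total diet effect is then −3 × ρ × shift, and the same bias works against it. With ρ = 0.5 and shifts 0, 1.5 and 1.5, a total effect of −2.25 appears as −2.25 + 1.54 = −0.71 in high compliers and −2.25 + 1.26 = −0.99 in low compliers, so 31% and 44% are kept. A real effect is partly hidden.

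**The case against.** The strongest reply is that the SAP speaks of dietary adherence, and adherence to three different diets is naturally judged diet by diet. On that reading the cut would be arm-specific, and with equal correlations the bias is about 0. The example markers also suit different diets, several markers are to be combined, and the model adjusts for baseline liver fat. No single figure above can therefore be taken as the expected bias. All of this stands, and the numbers are only an illustration. It does not remove the point: the SAP does not state an arm-specific rule, and such a rule would balance subgroup sizes without making the contrasts randomised.

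A second reply is that the protocol may define compliers. The SAP refers to the protocol for details of the diets, and a definition there would fill the gap in the rule. It would not change the sentence in 5.2 that applies the between-diet analysis to this split.

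A reader might infer that hiding a real effect is the likelier error, because the introduction places lipogenesis on the causal path. The documents do not support that ranking. The hypothesis is stated for the customized diet only and is silent on the Nordic diet against control. DHA is not among the section 4.3 fatty acids, and linoleic acid (18:2n-6) appears there only as a ratio denominator.

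A reader might also infer that the trial's main conclusion is at risk. It is not: the primary analysis uses all randomised subjects without regard to compliance, and the SAP announces no efficacy claim based on compliers.

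**Conclusion.** The point holds, as a matter for a secondary subgroup analysis. Followed as written, sections 4.2, 5.2 and 6.1 give diet contrasts within strata formed after randomisation by markers that the diets are expected to change. This is more than missing detail, because the prescribed analysis is itself unsuited to the split.

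Size and direction cannot be fixed from the SAP. Under the assumptions listed, the bias runs from about 0 (arm-specific cuts, equal correlations) to false differences of about 0.3 to 1.5 percentage points (one common median cut across three arms, no diet effect), not always equal in the two strata. For scale, the SAP regards 2 points as clinically relevant. HbA1c and lipids were not computed, since the SAP gives no SD for them.

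**What to change.** - In 5.2, exempt Compliers from the sentence that applies the full-population analysis to all subgroups.
- In 5.2 and 4.2, label the complier analysis exploratory and non-randomised, and state that no between-diet efficacy conclusion will rest on it.
- Examine biomarker change against outcome change within each diet arm. Section 6.3 already plans correlations of fatty-acid changes with changes in liver fat and HbA1c; specifying that they are done within arm is enough. These too should be described as non-randomised.
- If a high/low split is still shown, fix the markers, their expected direction for each diet, the threshold, and whether the cut is arm-specific, before outcome data are seen.

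The cost is SAP wording only, with no new data and no change to the primary analysis. The downside is that complier results can no longer be read as between-diet effects.

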## 6. Analyses

Normally distributed variables will be presented as mean  $\pm$  SD and skewed distributed variables will be presented as median (IQR). Continuous variables will be tested for normality using the Shapiro-Wilk W test and skewed data ( $W < 0.95$ ) will be logarithmically transformed or analyzed non-parametrically, where appropriate. Homogeneity of variances between groups will be examined visually. Categorical variables will be presented as counts or percentages (%). An  $\alpha$ -value of 0.05 is set as the significance level.

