## **6.2 Secondary and exploratory outcomes**

For secondary and exploratory outcomes GLMs will be applied using  $\Delta$ values between baseline and month 12 for each continuous variable (see point 4.2 and 4.3) as dependent variables and type-2 diabetes status (yes/no), gender (male/female) and baseline outcome values as included covariates in the model. Outcome values from 6 months follow-up will be presented descriptively.

The GLM will be applied for the ITT-population (defined above) as well as for the PP-population (defined above) for HbA1c, LDL cholesterol, triglycerides and systolic- and diastolic blood pressure. For the remaining secondary and exploratory outcomes, a PP-population will be used. Independent samples post-hoc t-tests will follow if between-group statistical significance is observed.

Treatment effects will be presented as mean or median differences (%) with 95% confidence intervals and with corresponding p-values.

When assumptions of the GLM are not satisfied, the Willett's residual method will be applied (3), followed by Mann-Whitney U post-hoc tests.

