## **7. Missing data**

Missing numerical and categorical data (including both dependent- and explanatory variables) will be imputed using the technique of multiple imputation by chained equations (MICE). Categorical data will be coded into dummy variables. Number of missing values for each variable of which have been imputed will be presented as n/% for each group separately and in total.

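### The SAP asks whether diet response differs between subgroups, but plans only separate within-subgroup analyses and no test or estimate of the difference

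*SAP*

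**What the plan says.** **The question.** Section 1 lists among the aims: "Investigate gene-diet interactions, especially if common gene variants (e.g. in PNPLA3) known to increase liver fat and dyslipidemia, may modify the dietary effects". Section 4.2, in the entry on prespecified subgroups, explains its purpose: "We will assess whether response to diets in liver fat, HbA1c and blood lipids differ between gender, high vs low compliers, genotype", and goes on to diabetes and NAFLD status. Both are questions about effect modification.

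**The method.** Section 5.2 splits participants in two on each of five factors and states: "All subgroup analyses will be conducted as described for the analyses of the full study population". The full-population analysis is the GLM of sections 6.1 and 6.2. For the primary outcome it has "treatment group as factor and type-2 diabetes status (yes/no), gender (male/female) and baseline liver fat content (%) as included covariates". The secondary-outcome model adjusts for the same two factors and the baseline value. Post-hoc t-tests follow a significant omnibus result. If assumptions fail, section 6.1 says: "When assumptions of the GLM are not satisfied, the Willett's residual method will be applied, followed by Mann-Whitney U post-hoc tests". Results are reported as differences with 95% confidence intervals and p-values. Section 6.3 adds only correlations between changes.

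**Populations.** Liver fat, HbA1c, LDL cholesterol and triglycerides are analysed in both ITT and PP. For the other lipids section 6.2 applies: "For the remaining secondary and exploratory outcomes, a PP-population will be used".

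**The concern.** Whether response differs between two groups of participants is a question about the difference between two diet effects. The plan estimates each effect separately and stops there. No section gives the difference, its confidence interval or a test of it. NAFLD status and genotype enter no model at all; diabetes status and gender enter only as main effects.

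The practical risk lies in how the results will be read. Each stratum gets its own p-value and its own significance-gated post-hoc tests. A report that a diet worked in one genotype but not the other would then be easy to write, though it can arise readily when the diets work equally well in both. At stake are the gene-diet aim and the stated purpose of the subgroup entry, not the primary comparison.

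**Working it through.** **1. The plan's own figure.** Section 2.1 uses Lehr's formula with SD 3 and a 2-point difference: 16 × (3/2)² = 36 per group, as stated (reading the SAP's β = 0.80 as 80% power). With 25% drop-out, 36/0.75 = 48, close to the 50 randomized per arm. So 36 to 50 per arm are available before any subgroup split.

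**2. Inputs for the illustration.** SD 3, the 2-point effect and α = 0.05 come from sections 2.1 and 6. Two things are assumed: both experimental diets have the same 2-point effect in both strata (section 2.1 also assumes the two diets are equal), and the stratum sizes, which the SAP does not give.

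**3. Power within a stratum.** For the 2-df omnibus F test with arm means 0, 2, 2 and n per arm, the noncentrality is n × [(4/3)² + 2 × (2/3)²]/SD² = n × (8/3)/SD². At SD 3:
- n = 25: 25 × 2.667/9 = 7.41, power 0.662
- n = 18: 5.33, power 0.506
- n = 29: 8.59, power 0.734
- n = 7: 2.07, power 0.203

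**4. Chance that exactly one stratum is significant.** This is p₁(1 − p₂) + p₂(1 − p₁). For 25/25 it is 2 × 0.662 × 0.338 = 0.447. For 29/7 it is 0.734 × 0.797 + 0.203 × 0.266 = 0.639.

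| n per arm in the two strata | SD 3 | SD 2.60 | SD 2.42 | SD 2.12 | SD 1.95 |
|---|---|---|---|---|---|
| 18/18 | 0.500 | 0.463 | 0.419 | 0.298 | 0.211 |
| 25/25 | 0.447 | 0.329 | 0.255 | 0.127 | 0.068 |
| 25/12 | 0.550 | 0.532 | 0.498 | 0.396 | 0.315 |
| 33/17 | 0.511 | 0.415 | 0.349 | 0.219 | 0.146 |
| 29/7 | 0.639 | 0.671 | 0.667 | 0.620 | 0.568 |
| 40/10 | 0.657 | 0.615 | 0.574 | 0.472 | 0.396 |

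SD 2.60 and 2.12 are 3 × √0.75 and 3 × √0.50, that is, covariates explaining 25% or 50% of the variance. SD 2.42 and 1.95 are the earlier-trial values in section 2.1.

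A simulation of the within-stratum F test at 18 and 25 per arm gave 51% and 66% power per stratum and 51% and 45% discordance, in agreement with the table.

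**5. What an interaction test could deliver.** If both experimental diets' effects differ by d between strata of a and b per arm, the 2-df interaction has noncentrality [ab/(a + b)] × (2d²/3)/SD². For d = 2 and SD 3, 18/18 gives 9 × 2.667/9 = 2.67. Pooled-variance power is then 28% (18/18), 38% (25/25), 19% (29/7) and 26% (40/10). Simulation with HC3 robust standard errors gave 26%, 37%, 18% and 25%; for d = 4 it gave 81%, 92%, 58% and 76%.

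For one diet against control at an even split, the standard error is 3 × √(2/a + 2/b): 1.41 at 18/18 and 1.20 at 25/25. Multiplied by 2.80 (= 1.96 + 0.84), the difference in effect detectable with 80% power is about 4.0 and 3.4 points.

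**6. Unequal variances.** With assumed stratum SDs of 3.5 and 1.5 and uneven splits, the pooled interaction test had a simulated type I error from 0.1% to 31%. The HC3 version without covariates gave 4.5-6.2%, with up to 6.7% in a repeat run; with covariates it gave 4.1-7.1%. None of these runs included imputation.

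**The case against.** **The subgroup outcome is not left without analysis.** A reader might infer that a listed secondary outcome has no planned inference at all. The SAP does not support that. The outcome as listed in section 4.2 is between-group change within subgroups, and the stratum GLMs are inference for exactly that. What lacks a method is the explanatory statement attached to it, and the gene-diet aim in section 1.

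**The SAP does not plan the misuse.** A reader might also infer that differential response will be declared whenever one stratum is significant and the other is not. No section says so. Stratum estimates with confidence intervals permit an informal comparison. The discordance figures therefore show why stratum p-values cannot answer the question; they are not the error rate of a planned procedure.

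**The magnitude is soft.** This stands. The splits and the variance explained are assumed, the range is wide, and the SD 3 column ignores the planned baseline adjustment. The illustration does not suit NAFLD status, because low baseline liver fat limits how far it can fall. The logical gap does not depend on these figures.

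**Low power is a reason not to test.** It is a reason to label the result exploratory. An imprecise estimate of the difference still addresses the stated question, whereas two separate p-values do not.

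**Robust standard errors rest on invented SDs.** Partly fair: the 3.5 and 1.5 are assumptions. Section 6 does provide a check ("Homogeneity of variances between groups will be examined visually"), but only visually and between groups, with no stated consequence for a comparison across strata.

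**Conclusion.** The concern holds in this form: sections 1 and 4.2 pose an effect-modification question, section 5.2 fixes a within-stratum method, and no section supplies a test or estimate of the difference between strata. This is internal to the SAP and not a matter left to the protocol.

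The consequence can be substantial for liver fat at the planning SD: 45-50% discordance at even splits and 64-66% near 80:20 under identical true effects. It falls to 7-57% at SD 1.95, depending on the split. The primary analysis is untouched, so this is a change that should be made rather than one that threatens the trial's main result.

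A separate and smaller point: section 5.2 defines compliers by biomarker changes from month 0 to month 12. The diets may cause those changes, and palmitoleic acid (16:1n-7) is itself an exploratory outcome in section 4.3. Diet contrasts within complier strata are therefore not randomized comparisons, and an interaction term would not cure that.

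**What to change.** Keep the last sentence of section 5.2 for the within-stratum estimates and add:

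> For each baseline factor (type-2 diabetes status, gender, NAFLD status, PNPLA3 genotype) the diet × factor interaction, with the factor's main effect where not already included, is added to the full-population GLM, in the same populations and on the same outcome scale as the main analysis of that outcome. The interaction estimates with 95% CIs and the 2-df interaction p-value are reported. Claims of differential response rest on the interaction, not on stratum p-values, and are exploratory. Heteroscedasticity-robust standard errors are used where variances differ between strata.

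In section 7, state that the imputation model for the ITT analyses includes the diet × factor term. In section 5.2, retain the complier analysis but label it descriptive.

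**Cost.** Wording, one interaction per baseline factor, a wider imputation model and a stated rule for pooling the 2-df test over imputed data sets. Where an outcome moves to the non-parametric fallback, the SAP should also say in advance how, or whether, the interaction will be reported.

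**Downsides to state in the SAP.** Power is about 18-37% for a 2-point difference in effect at SD 3, so a non-significant interaction is not evidence of equal response. The tests are not adjusted for multiplicity: eight outcomes (liver fat, HbA1c, six lipids) by four factors give 32 pairs. With four outcomes run in both ITT and PP, that is 4 × 12 = 48 tests.
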